### 3. OVERALL STUDY DESIGN

This open-label extension study will evaluate the safety, tolerability, and PD effects of up to 60 months of ACE-536 treatment in patients with low or intermediate-1 risk MDS previously treated with ACE-536 for up to 3 months in study A536-03.

#### 3.1. Study Design

Patients in all cohorts will receive ACE-536, administered subcutaneously (SC), every 3 weeks for up to 87 cycles or up to 1825 days, whichever occurs first. Dose titration(s), delay(s) and dose reduction(s) may be required for individual patients as outlined in the Individual Dose Modification Rules (protocol Section 10.8).

The base study A536-03 is a phase 2, open-label, ascending dose study to evaluate the effects of ACE-536 on anemia in patients with low or intermediate-1 risk MDS who are not currently receiving treatment with an erythropoiesis-stimulating agent (ESA). A total of up to 153 patients may be enrolled in the base study A536-03 and may be eligible for study A536-05.

Consenting patients that meet the A536-05 eligibility criteria may immediately roll over from A536-03 to study A536-05. These patients will forego the Post-Treatment Follow-up (PTFU) and End of Study (EOS) visits of A536-03 to begin study A536-05. For these patients, C1D1 of A536-05 may take place 28 ( $\pm$  7) days after the last dose administered in the base study A536-03, which may coincide with the patient's A536-03 End of Treatment (EOT) visit. These patients will be considered "patients without treatment interruption." Patients enrolled in expansion cohorts 2 and 3 in Study A536-03 must meet the "patients without treatment interruption" criteria to be considered for the A536-05 study, unless otherwise prospectively approved by the sponsor.

Patients who complete the EOS visit for the base study A536-03 prior to C1D1 of A536-05 are considered "patients with treatment interruption." These patients will have a 28-day screening period to allow them to be re-assessed for eligibility by meeting additional inclusion criteria, as defined in protocol Section 9.2.

Patients who have completed the EOT visit for the base study A536-03 but have not reached the EOS visit (i.e., patients in the follow-up period for A536-03), may still participate, but should be treated as patients with treatment interruption and should not begin study A536-05 C1D1 until they have completed their A536-03 EOS visit so that new baseline assessments can be measured. Patients transfusion status (LTB or HTB) are defined in [Section 5.1](#). Each HTB patient will have a "pre-transfusion hemoglobin threshold" for requiring transfusion, which will be calculated based on transfusion history and will be used for determining when to transfuse during the study. The baseline pre-transfusion hemoglobin threshold will be the mean of all documented pre-transfusion hemoglobin values during the 12 weeks prior to C1D1 of base study A536-03 for patients without treatment interruption, or prior to C1D1 of study A536-05 for patients with treatment interruption. During treatment, if the pre-transfusion hemoglobin level is increased by  $\geq$  1 g/dL compared to the baseline pre-transfusion hemoglobin threshold for that patient,

transfusion should be delayed by a minimum of 7 days and/or the number of units transfused should be reduced by 1 or more RBC units. Patients should not be transfused if hemoglobin is  $\geq 9$  g/dL unless indicated for symptoms related to anemia or other reasons at the investigator's discretion.

Patients will participate in the extension study A536-05 for approximately 8 years, including a 28-day screening period, a 60-month treatment period, and a 3-year follow-up period.

A patient without treatment interruption may continue to be dosed with ACE-536 at the same dose level administered at their last dose in study A536-03, unless a dose reduction is required based upon patient dose modification rules from study A536-05.

All patients with treatment interruption will be initially treated with ACE-536 at an assigned starting dose level of 1.0 mg/kg, which has been deemed to be safe, well tolerated, and at least minimally effective by the Safety Review Team (SRT) based on data from the base study A536-03. Examples of possible starting dose levels with respective dose levels for modification (reductions and titrations) are shown in the table below for reference.

#### **Possible Starting Dose Levels with Dose Level Modifications (Reductions and Titrations)**

3 rd Dose Reduction	2 nd Dose Reduction	1 st Dose Reduction	Starting Dose Level	1 st Dose Titration	2 nd Dose Titration	3 rd Dose Titration
	0.125 mg/kg	0.25 mg/kg	0.50 mg/kg	0.75 mg/kg	1.0 mg/kg	1.33 mg/kg
0.125 mg/kg	0.25 mg/kg	0.5 mg/kg	0.75 mg/kg	1.0 mg/kg	1.33 mg/kg	1.75 mg/kg
0.25 mg/kg	0.5 mg/kg	0.75 mg/kg	1.0 mg/kg	1.33 mg/kg	1.75 mg/kg	
0.5 mg/kg	0.75 mg/kg	1.0 mg/kg	1.33 mg/kg	1.75 mg/kg		
0.75 mg/kg	1.0 mg/kg	1.33 mg/kg	1.75 mg/kg			

- Starting dose level for patients with treatment interruption is 1.0 mg/kg.
- Starting dose level for patients without treatment interruption will be last dose level administered in study A536-03 unless a dose reduction is required based upon patient dose modification rules from study A536-05.
- Patients may be titrated up and down dose levels as required per protocol to meet dose modification and titration rules.
- Patients who require more than 2 dose reductions due to an AE should be discontinued from treatment and complete the EOT, PTFU, LTFU, and EOS visits.
- The maximum dose titration will not exceed 1.75 mg/kg.

### **3.2. Treatment Discontinuation**

Patients will be informed that they have the right to discontinue treatment and/or withdraw from the study at any time for any reason without prejudice to their medical care.

A patient may be discontinued from treatment for any of the following reasons:

- Patient's request

- Patient's unwillingness or inability to comply with the protocol
- Pregnancy
- Use of prohibited medication (e.g., ESA)
- Medical reason or adverse event, at the discretion of the investigator and/or the medical monitor
- Lack of effect (e.g., worsening anemia for LTB patients as evidenced by sustained reduction in Hgb by  $\geq 2$  g/dL over 8 weeks or transfusion dependence), to be discussed with the medical monitor
- Disease progression (per IWG criteria for altering natural history of MDS [Cheson et al, 2006]):
  - For patients with 5-10% blasts, a 2nd bone marrow sample should be collected within 4 weeks for clinical assessment (e.g., cytomorphology, cytogenetics) to confirm progression before discontinuing patients from treatment)
- Persistent increase in white blood cell (WBC) count as per Individual Dose Modifications in protocol Section 10.8
- Presence of  $\geq 1\%$  blasts in peripheral blood as per Individual Dose Modifications in protocol Section 10.8
- Hypersensitivity reaction to study drug
- At the discretion of the sponsor (e.g., termination of the study or a dose level)

A patient may be withdrawn from the study for any of the following reasons:

- Patient's request
- Patient's unwillingness or inability to comply with the protocol
- Death
- Loss to follow-up
- At the discretion of the sponsor (e.g., termination of the study)

The reasons for study withdrawal and/or treatment discontinuation must be recorded in the patient's CRF. The investigator must notify the sponsor, the medical monitor and the contract research organization (CRO) immediately when a patient has been discontinued/withdrawn due to an AE. Patients who discontinue treatment early should complete the EOT follow-up visit at the time of discontinuation, then complete the Post-Treatment Follow-up (PTFU) visit 2 months  $\pm$  7 days after the last dose of ACE-536, the LTFU visits every 3 months, and finally the EOS visit 3 years after the last dose of ACE-536.

### 3.3. Sample Size

There is no formal sample size calculation for the study although up to 153 patients may participate from the A536-03 study.

## 4. ANALYSIS POPULATIONS

### 4.1. Intent-to-Treat (ITT) Population

The intent-to-treat (ITT) population will consist of all patients who have received at least 1 dose of ACE-536 in A536-05 study. This population will be used for all efficacy analyses.

For patients who directly rolled over from A536-03 study, both A536-03 study and A536-05 study data will be included for the analysis.

For interrupted patients, only A536-05 study data will be included for the analysis.

### 4.2. Safety Population

Same as ITT population.

### 4.3. Pharmacokinetics (PK) Population

The pharmacokinetics population will include all patients who have received at least 1 dose of ACE-536 during Study A536-05 and have sufficient serum ACE-536 values for PK analysis.

## 5. STATISTICAL METHODOLOGY

### 5.1. Definitions

#### Transfusion Status

For patients without treatment interruption, transfusion status (LTB or HTB) will carry-over from the base study A536-03. For patients with treatment interruption, transfusion status will be reassessed prior to C1D1 of study A536-05. Transfusion status for all patients is defined as follows for all patients:

- LTB patients are defined as patients who require a transfusion of < 4 units of RBCs in the 8 weeks prior to C1D1
- HTB patients are defined as patients who require a transfusion of  $\geq 4$  units of RBCs in the 8 weeks prior to C1D1

#### Baseline

For patients who roll over to Study A536-05 without interruption, the baseline for Study A536-03 will be used as the baseline for Study A536-05.

For patients who enter Study A536-05 with interruption, the last value on or before the first dose of Study A536-05 will be considered as the baseline unless otherwise specified. For baseline assessments that are not scheduled in A536-05 study or data collection is inadequate at the baseline of Study A536-05, the baseline value for Study A536-03 will be used as the baseline for Study A536-05.

**Baseline Hemoglobin**

Baseline hemoglobin will be an average of hemoglobin measurements within 28 days of Cycle 1 Day 1, excluding measurements within 7 days following RBC transfusion.

**Baseline Transfusion Burden**

Baseline transfusion burden will be calculated as the total amount of RBC transfusion during the 8 weeks prior to Cycle 1 Day 1.

**Baseline EPO and Other Lab Parameters**

Baseline erythropoietin (EPO) is defined as the maximum test value within 28 days of Cycle 1 Day 1.

For all other lab parameters, baseline is defined as the last observation on or prior to Cycle 1 Day 1.

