PD assessments for hematological markers showed increases in hemoglobin levels at the 0.125 mg/kg dose level and more consistently at the 0.25 mg/kg dose level. Small increases in reticulocyte count and EPO levels were also observed at the two higher dose levels of ACE-536 investigated. A small decrease in serum follicle-stimulating hormone (FSH) levels was observed at 0.25 mg/kg. These data support further studies of ACE-536 in conditions associated with ineffective erythropoiesis and anemia.

Two phase 2 studies with ACE-536 are ongoing. Study A536-03 is entitled, "A Phase 2, Open-Label, Ascending Dose Study of ACE-536 for the Treatment of Anemia in Patients with Low or Intermediate-1 Risk Myelodysplastic Syndromes (MDS)". Study A536-04 is entitled "A Phase 2, Open-Label, Ascending Dose Study to Evaluate the Effects of ACE-536 in Patients with β -Thalassemia". Preliminary results from these studies and additional information regarding the completed Phase 1 study can be found in the current version of the IB.

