#### **5.8.2.7. Erythropoietin and Immature RBC Parameters**

Blood samples relating to erythropoietin parameters including serum erythropoietin levels, reticulocytes and nucleated RBCs will be taken at Day 1 of Cycle 1 and every 4 subsequent cycles, EOT, PTFU and EOS visits. Descriptive statistics of observed values, absolute and percentage change from baseline values at each postbaseline visit will be presented. Plots of erythropoietin parameters for mean observed values, mean change and mean percentage change from baseline over time will be presented.

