**7.2. Appendix 2: Schedule of Events for Study 03**

	Screen	Treatment Period															Follow up period			
		Cycle 1				Cycle 2			Cycle 3			Cycle 4			Cycle 5			EOT 	Post-Treatment Follow Up	EOS 
		C1D1 	C1D8	C1D1 1	C1D1 5	C2D1 	C2D8	C2D1 5	C3D1 	C3D8	C3D15	C4D1 	C4D8	C4D15	C5D1 	C5D8	C5D15			
		Day -28	Day 1	Day 8 (± 1d)	Day 11 (± 1d)	Day 15 (± 1d)	Day 22 (± 2d)	Day 29 (± 2d)	Day 36 (± 2d)	Day 43 (± 2d)	Day 50 (± 2d)	Day 57 (± 2d)	Day 64 (± 2d)	Day 71 (± 2d)	Day 78 (± 2d)	Day 85 (± 2d)	Day 92 (± 2d)	Day 99 (± 2d)	Day 113 (± 7d)	Day 141 (± 7d)
Informed consent	X																			
Inclusion/Exclusion	X	X																		
Medical history	X																			
FACT-An Questionnaire 	X															X		X 	X	
Physical examination	X	X				X			X			X			X			X	X	
Vital signs 	X	X	X		X	X	X	X	X	X	X	X	X	X	X	X	X			
ECOG Status	X							X			X							X	X	
ECG (12 lead)	X					X												X		
Bone marrow aspirate/biopsy 	X							X										X		
Serum iron studies 	X	X				X	X		X			X			X			X	X	
Serum folate and B12	X																			
Erythropoietin levels	X	X	X		X	X						X						X	X	
Hematology 	X	X	X		X	X	X	X	X	X	X	X	X	X	X	X	X	X		
Peripheral blood smear	X	X				X								X			X			
Serum chemistry 	X	X			X	X	X		X	X		X	X		X	X		X		
Urinalysis and Urine Chemistry 		X				X						X						X	X	
Anti-drug antibody 		X										X						X	X 	
PK collection		X	X	X	X	X	X					X			X	X	X	X	X	
PD biomarkers 		X				X			X			X			X			X	X	
Bone biomarkers 		X										X						X		
Pregnancy test 	X	X				X			X			X			X			X	X	
Evaluate transfusion frequency 	X	X				X			X			X 			X			X	X	
Concomitant medications and AEs	X	X	X	X	X	X	X	X	X	X	X	X	X	X	X	X	X	X		
Administer ACE-536 		X				X 			X 			X 			X 					

 **Vital signs:** Weight, heart rate, systolic and diastolic blood pressure, respiration rate and temperature (measured in degrees Celsius). Height is measured only at Screening.

 **Study procedures** must be done prior to administration of study drug.

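### For roll-over patients, baseline EPO is a maximum, so single later EPO values tend to fall below it even with no drug effect

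*SAP*

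**What the plan says.** SAP 5.1 gives EPO its own baseline rule: "Baseline erythropoietin (EPO) is defined as the maximum test value within 28 days of Cycle 1 Day 1". The next sentence treats every other laboratory parameter differently: "For all other lab parameters, baseline is defined as the last observation on or prior to Cycle 1 Day 1". Hemoglobin, defined just above, uses an average.

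For patients who roll over without interruption, SAP 5.1 says "the baseline for Study A536-03 will be used as the baseline for Study A536-05", and SAP 4.1 adds that "both A536-03 study and A536-05 study data will be included for the analysis". In the A536-03 schedule (SAP Appendix 2), the row "Erythropoietin levels" is marked at Screening, C1D1, C1D8, C1D15 and C2D1 (Day 22), and again later.

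Interrupted patients take their baseline from A536-05. That schedule (Protocol Section 2, SAP Appendix 3) has EPO at C1D1 but not at Screening, and next at C5D1.

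SAP 5.8.2.7 says EPO samples "will be taken at Day 1 of Cycle 1 and every 4 subsequent cycles, EOT, PTFU and EOS visits", and of the analysis: "Descriptive statistics of observed values, absolute and percentage change from baseline values at each postbaseline visit will be presented". Mean change and mean percentage change are also plotted. SAP 5.8.4 uses baseline EPO for subgroups cut at 100, 200 and 500, and in logistic models as a continuous factor and cut at 100 and 200 IU/L. The SAP gives no reason for the maximum, and SAP 5.13 does not list it among the changes from the protocol.

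**The concern.** The two sides of the comparison are built differently. For a roll-over patient the baseline is the highest of at least two scheduled values, and each later value is one ordinary draw. Selecting the highest value picks up upward noise that the later value does not share, so the change is pushed downward with no drug effect at all.

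EPO is a named secondary pharmacodynamic objective. The study has no control arm against which such a shift could cancel. Roll-over and interrupted patients also carry different amounts of this bias, so pooling them mixes two definitions.

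A second problem lies in the window. The EPO sentence does not say that only values before the first dose count. Read literally, three on-treatment A536-03 draws would enter the baseline.

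**Working it through.** The plan states no figure here, so there is none to reproduce. The check asks what change is expected when the drug does nothing.

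**Inputs from the documents**
- Roll-over patients have k = 2 baseline values (Screening, C1D1) if only pre-dose draws count, and k = 5 if C1D8, C1D15 and C2D1 also count.
- Interrupted patients have k = 1 by schedule.
- Each later visit contributes one value.

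**Inputs assumed**
- The within-patient CV of EPO is not given. It is taken as 20% to 50%.
- Draws are independent and lognormal, except where a correlation is stated.

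**Step 1: expected absolute change.** For k independent normal values, the expected change is -E[max of k standard normals] × SD.
- k = 1: 0.
- k = 2: -1/√π = -0.56 SD.
- k = 5: -1.16 SD.

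The chance that a later value lies below the baseline is k/(k+1): 1/2 for one value, 2/3 (67%) for two and 5/6 (83%) for five.

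**Step 2: percentage change with two draws.** The log-scale SD is s = √ln(1 + CV²). The median of Z0 - max(Z1, Z2) is -0.555, so the median percentage change is exp(-0.555 s) - 1.
- CV 20%: s = 0.198, so exp(-0.110) - 1 = -10%.
- CV 50%: s = 0.472, so exp(-0.262) - 1 = -23%.

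Simulation with one million or more patients per setting agrees, and adds the means:

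| k = 2, independent | CV 20% | CV 30% | CV 50% |
|---|---|---|---|
| Mean absolute change, % of patient mean | -11 | -16 | -26 |
| Median percentage change | -10 | -15 | -23 |
| Mean percentage change | -8 | -9 | -8 |

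Mean percentage change moves less because dividing by a noisy baseline biases the ratio upward. At CV 70% it is about -2%, and at CV 100% it is +11%.

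**Step 3: correlated baseline draws.** Screening and C1D1 are close in time. With correlation ρ between them and an independent later value, the expected fall is √((1-ρ)/π) SD. At an assumed ρ = 0.5 this is √(0.5/π) = 0.40 SD. The median percentage change becomes about -7.5% at CV 20% and -17% at CV 50%. The mean percentage change becomes about -4% and +2%.

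**Step 4: pooling.** If a share f of patients roll over, the pooled mean absolute change is f times the k = 2 figure. At CV 30%, f = 0.5 gives 0.5 × -16% = -8%. The documents do not give f.

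**Step 5: the window read literally.** With k = 5, the median percentage change is -20% at CV 20% and -42% at CV 50%. Values at C1D8, C1D15 and C2D1 would be members of the set whose maximum is the baseline, so change at those visits could never be above zero.

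**Step 6: cut-points.** Take a true level of 90 IU/L and CV 30%. One value exceeds 100 with probability 0.36. The maximum of two does so with probability 1 - 0.64² = 0.59, and the maximum of five with 1 - 0.64⁵ = 0.89.

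**Step 7: the proposed baseline.** With the last pre-dose value, the simulated absolute change and median percentage change are both zero within simulation error. Mean percentage change is +4% at CV 20% and +9% at CV 30%, so the median or the log ratio is the better summary.

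**The case against.** In favor of the plan as written, the following can be said.

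- **Reach.** A reader might infer that every patient's change is biased. The schedules do not support that, because interrupted patients have one scheduled EPO value near A536-05 C1D1. This stands, and it limits the point to roll-over patients.
- **Size.** The CV and the independence of the draws are assumptions, and mean percentage change, which the plan also reports, moves little. This stands. The downward direction for absolute change and median percentage change does not depend on the CV.
- **Post-dose draws.** A reader might take -20% to -42% as the effect size. That needs a two-sided window. SAP 5.1 ties the general baseline rule for interrupted patients to the first dose, 28 days is also the screening window, and Protocol Appendix 5 places its pre-treatment counts before Day 1. A pre-dose intention is plausible. The wording is open, but it does not show that on-treatment values will be used.
- **Masking a drug effect.** A reader might infer that the rule hides or reverses the rise seen in phase 1. Protocol 7.3 says only "Small increases in reticulocyte count and EPO levels were also observed at the two higher dose levels", in healthy postmenopausal women and with no figure, so the two sizes cannot be compared. Observed values are also summarized, plotted and listed, and comparisons between later visits are unaffected.
- **Cut-points.** A prespecified maximum is a legitimate classification rule, and a last value also misclassifies (0.36 in Step 6). This stands for the cut-points, but it does not justify the maximum as the reference for change.
- **Hemoglobin.** Its baseline window has the same open wording, but it is an average, so this bias does not carry over.

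**Conclusion.** The point holds for patients who roll over without interruption. By construction, the planned absolute change and median percentage change in EPO are biased downward: about 0.56 within-patient SD for two independent pre-dose draws, or a median of about -10% to -23% at an assumed CV of 20% to 50%. The fall is smaller if the baseline draws are correlated. Mean percentage change falls only about 8% to 9% over that CV range with independent draws. Interrupted patients have no such bias by schedule, so the pooled bias scales with the unknown roll-over share.

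The open window is a separate wording defect whose literal reading would roughly double the bias. The documents do not establish that this reading is intended, nor that any real EPO effect would be hidden or reversed. The consequence is confined to a descriptive secondary pharmacodynamic endpoint and the EPO classifications. There is no formal testing, and the primary safety objective is untouched. It should be corrected before the analysis is run.

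**What to change.** In SAP 5.1, define baseline EPO for change from baseline as the last value on or before the first dose, as for the other laboratory parameters, or as the mean of the pre-dose values. For roll-over patients, say that the first dose meant is the one in A536-03. In SAP 5.8.2.7, lead with the median or the log ratio for percentage change.

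If the maximum is wanted for the 100/200/500 subgroup cut-points and the 100/200 logistic cut-points, restrict it to pre-dose values, hold it as a separately named variable, and state which version the continuous logistic term uses.

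The cost is a few sentences in the SAP and one extra derived variable. No new data are needed.

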24.5. Appendix 5: International Working Group (IWG) Criteria - Erythroid Response Evaluation¹

Hematologic Improvement (HI) ^a	Response Criteria (Responses must last at least 8 weeks)
Erythroid response (Hi-E) (pretreatment Hgb < 11 g/dL)	Hgb increase of ≥ 1.5 g/dL for patients not transfused; or, as defined by having received less than 4 units of RBCs within 8 weeks of Cycle 1 Day 1 Reduction by ≥ 4 units of RBCs transfused (for a Hgb ≤ 9.0 g/dL) during any 8-week period on study, compared with the 8-week period prior to study day 1
Platelet response (HI-P) (pretreatment, $< 100 \times 10^9/L$)	Absolute increase of $\geq 30 \times 10^9/L$ for patients starting with $> 20 \times 10^9/L$ platelets Increase from $< 20 \times 10^9/L$ to $> 20 \times 10^9/L$ and by at least 100%
Neutrophil response (HI-N) (pretreatment, $< 1.0 \times 10^9/L$)	At least 100% increase and an absolute increase $> 0.5 \times 10^9/L$

^a Pre-treatment counts are averages of at least 2 measurements (not influenced by transfusions) ≥ 1 week apart within 28 days prior to Day 1.

Hgb: indicates hemoglobin; RBC: red blood cell; HI: hematologic improvement.

24.6. Appendix 6: National Cancer Institute (NCI) Common Terminology Criteria for Adverse Events (CTCAE) Version 4.0

See <http://evs.nci.nih.gov/ftp1/CTCAE/CTCAE>

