#### **5.8.2.4. HI-P and HI-N Response Rate**

Platelet (HI-P) and neutrophil (HI-N) response will be defined for patients with abnormal baseline values, following IWG 2006 criteria.

HI-P response will be defined for patients with baseline platelet count  $< 100 \times 10^9/\text{L}$ :

- For patients with baseline  $\geq 20 \times 10^9/\text{L}$ , an absolute mean increase of  $\geq 30 \times 10^9/\text{L}$  during any rolling 8-week interval on treatment;
- For patients with baseline  $< 20 \times 10^9/\text{L}$ , mean value of  $> 20 \times 10^9/\text{L}$  and mean percentage increase  $\geq 100\%$  during any rolling 8-week interval on treatment.

HI-N response will be defined for patients with baseline neutrophil count (ANC)  $< 1.0 \times 10^9/\text{L}$ :

- Mean percentage increase  $\geq 100\%$  and an absolute mean increase  $> 0.5 \times 10^9/\text{L}$  during any rolling 8-week interval on treatment compared with baseline.

The number and percentage of HI-N/HI-P responders will be presented. The HI-N and HI-P response will also be listed for each patient.

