### **5.8.7. Laboratory Evaluations**

Results from the following laboratory parameters, recorded at their respective time points will be summarized by time point:

**Hematology** (Screening, Day 1 of each cycle, End of Treatment, Post Treatment Follow Up and End of Study): RBC, white blood cell (WBC) with differential, hemoglobin, hematocrit, reticulocyte count, platelet count, mean corpuscular volume (MCV), mean corpuscular hemoglobin (MCH), mean corpuscular hemoglobin concentration (MCHC), red blood cell distribution width (RDW), and nucleated RBCs (nRBCs)

**Chemistry** (Screening, Day 1 of Cycle 1 and Day 1 of every other subsequent cycles, End of Treatment and End of Study): Sodium, potassium, aspartate aminotransferase (AST), alanine aminotransferase (ALT), lactate dehydrogenase (LDH), total bilirubin, direct bilirubin, alkaline phosphatase, blood urea nitrogen (BUN)/urea, creatinine, gamma-glutamyl transpeptidase (GGT), calcium, phosphorus, glucose, amylase, lipase, total protein, albumin, and uric acid

**Urine Analysis** (Day 1 of Cycle 1 and every 4 subsequent cycles, End of Treatment and End of Study): pH, specific gravity, protein, glucose, ketones, blood, leukocyte esterase, nitrite, microscopic examination (if performed)

**Urine Chemistry** (Day 1 of Cycle 1 and every 4 subsequent cycles, End of Treatment and End of Study): Microalbumin and creatinine; albumin/creatinine ratio

Categorical and numeric variables will be presented separately. Actual values and changes in hematology and biochemistry laboratory values from baseline will be summarized by time point. Shift tables for the hematology and biochemistry laboratory parameters comparing values above, within and below the normal reference range at baseline to the end of treatment visit will be presented using standard reference ranges.

Peripheral blood smears are taken at Screening, Day 1 of Cycle 1 and every 4 subsequent cycles, and at the end of treatment visit. These data will be listed only.

All laboratory values will be listed for all patients.

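### SAP 5.1 takes the single last platelet or neutrophil count as the HI-P/HI-N baseline, where Protocol Appendix 5 requires the mean of at least two, so a chance low count can be scored as a response

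*SAP*

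**What the plan says.** HI-N and HI-P response rates under IWG 2006 are secondary objectives (Protocol 8.2). Protocol Appendix 5 reproduces those criteria. Its footnote a, attached to the heading of the hematologic improvement column and so covering HI-E, HI-P and HI-N alike, reads: "Pre-treatment counts are averages of at least 2 measurements (not influenced by transfusions) ≥ 1 week apart within 28 days prior to Day 1".

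SAP 5.8.2.4 states: "Platelet (HI-P) and neutrophil (HI-N) response will be defined for patients with abnormal baseline values, following IWG 2006 criteria". It sets entry cut-offs (platelets below 100 x 10^9/L, ANC below 1.0 x 10^9/L) and response thresholds over any rolling 8-week interval, but gives no baseline rule of its own. The rule comes from SAP 5.1:

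- Hemoglobin: "Baseline hemoglobin will be an average of hemoglobin measurements within 28 days of Cycle 1 Day 1", leaving out values within 7 days after an RBC transfusion.
- EPO: the maximum in that window.
- Everything else, hence platelets and ANC: "For all other lab parameters, baseline is defined as the last observation on or prior to Cycle 1 Day 1".

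On which Day 1 applies, SAP 5.1 says: "For patients who roll over to Study A536-05 without interruption, the baseline for Study A536-03 will be used as the baseline for Study A536-05". SAP 4.1 adds that for direct roll-over patients the data of both studies are analyzed.

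SAP 5.13 lists the altered hemoglobin baseline among the changes from the protocol. It does not mention platelets or ANC.

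**The concern.** Three parts of the Appendix 5 rule are lost for platelets and ANC: the averaging, the one-week spacing and the exclusion of transfusion-influenced counts.

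The averaging matters most, because the baseline does two jobs in SAP 5.8.2.4. It decides whether the patient enters the denominator, and it is the reference for the rise. A count that happens to be low does both in the same direction: it brings in a patient whose usual level may be above the cut-off, and it makes a return to that level look like improvement. This is regression to the mean.

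The study has no control arm, so such responses cannot be separated from a drug effect, and the rates would be reported under the IWG label. Protocol 15.5 says departures from its analyses will be indicated in the SAP, yet a reader of 5.13 would not learn of this one.

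**Working it through.** **No figure to reproduce.** The documents give no expected rate, power or precision for HI-P or HI-N. The check is a comparison of the texts, two worked cases and a simulation.

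**Worked cases (illustrative counts, x 10^9/L).**

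- ANC 1.2, then 0.6 as the last value; on-study 8-week mean 1.2. SAP baseline 0.6: 1.2/0.6 = 2.0, so +100% and +0.6, a responder. Appendix 5 baseline (1.2 + 0.6)/2 = 0.9: 1.2/0.9 = 1.33, so +33% and +0.3, evaluable but not a responder.
- Platelets 104, then 68 as the last value; on-study mean 100. SAP baseline 68: +32, a responder (threshold +30). Appendix 5 baseline (104 + 68)/2 = 86: +14, not a responder.

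**Entry to the denominator.** With a true ANC of 1.3 and within-patient CV 20%, 11.0% of patients fall below 1.0 on one value against 3.6% on the mean of two. With true platelets of 120 and CV 20%, 20.6% fall below 100 against 10.9%.

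**Simulation, no drug effect.**

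From the documents: the entry cut-offs and response rules of SAP 5.8.2.4, 21-day cycles, and the ceiling of 153 patients. Appendix 5 requires responses to last at least 8 weeks, so each window is 4 visits (days 0 to 63).

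Assumed, because the documents do not give them: true ANC lognormal (median 1.6, log-SD 0.6); true platelets lognormal (median 150, log-SD 0.5); independent lognormal within-patient error; 17 visits, about one year. A patient is a false responder if evaluable and the best 4-visit mean meets the rule.

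| Endpoint, CV | One value | Mean of two |
|---|---|---|
| HI-N, 20% | 0.9% | 0.04% |
| HI-N, 30% | 12.9% | 3.7% |
| HI-N, 40% | 32.2% | 16.1% |
| HI-P, 10% | 1.9% | 0.3% |
| HI-P, 15% | 13.5% | 5.4% |
| HI-P, 20% | 29.9% | 17.0% |

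**Patients = 153 x evaluable share x false-response rate, central CV.**

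- HI-N: 153 x 0.261 x 0.129 = 5.2 against 153 x 0.240 x 0.037 = 1.4, a gap of 3.8.
- HI-P: 153 x 0.225 x 0.135 = 4.6 against 153 x 0.217 x 0.054 = 1.8, a gap of about 3 (4.7 against 1.8 before the rates are rounded).

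At the lowest CVs in the table the gaps are about 0.3 (HI-N) and 0.5 (HI-P) patients. At the highest they are about 8 and 5.

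**Sensitivity at central CV (one value / mean of two).**

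- Real visit pattern of roll-over patients, with the weekly A536-03 counts followed by 3-weekly visits: HI-N 12.5% / 3.2%, HI-P 13.0% / 5.2%.
- 9 visits: HI-N 8.9% / 2.1%, HI-P 9.5% / 3.2%.
- 87 visits: HI-N 24.4% / 9.8%, HI-P 24.8% / 13.0%.
- Other population medians or spreads: HI-N 9.1-20.7% / 2.4-6.1%, HI-P 8.8-22.7% / 3.5-9.3%.
- Serial error correlation 0.5: HI-N 16.3% / 11.3%, HI-P 17.3% / 13.5%, a gap of about 1 to 2 patients.
- The same 0.5 as a component that persists through all visits: HI-N 1.3% / 0.1%, HI-P 2.5% / 0.4%, under one patient each.

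The mean of two gave the lower rate in every setting listed.

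**The case against.** The strongest reply is that SAP 5.8.2.4 invokes IWG 2006, so a programmer could let that specific endpoint rule override the general default in 5.1 and average the counts. But 5.8.2.4 does not say so, while 5.1 is explicit. At best the SAP supports two derivations of one endpoint, which still has to be settled before database lock.

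Second, roll-over patients carry the A536-03 baseline, and the A536-03 analysis plan is not among the documents. It may already average platelets and ANC. That doubt stands for those patients, but the last-value rule is the only platelet and ANC rule this SAP contains.

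Third, the size rests on assumed CVs, distributions and error structure, and 153 is a ceiling. This stands: at low CV, or if most of the variation persists across visits, the gap is under one patient.

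Fourth, the baseline is only part of the cause. Because any rolling window may qualify, the mean of two still leaves about 10% (HI-N) and 13% (HI-P) false response over 87 visits. This also stands. Averaging reduces the problem but does not remove it.

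Finally, these are descriptive endpoints with no hypothesis test, reported as numbers and percentages, and 5.13 claims to list only major changes. That limits the priority. It does not justify reporting under the IWG label a rate whose baseline departs from the protocol's own IWG table without saying so.

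**Conclusion.** The concern holds. As written, the SAP replaces the averaged, transfusion-free baseline of Appendix 5 with a single last value for HI-P and HI-N, uses that value for both entry and response, and does not declare the change. The mismatch in the text is certain. The resulting bias is upward, but its size is not known from the documents: under the central assumptions it is 3 to 4 extra false responders per endpoint among at most about 34 to 40 evaluable patients, and across the assumed CVs it ranges from under 1 to about 8. The SAP should be corrected. Nothing here affects the primary safety objective.

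**What to change.** In SAP 5.1 or 5.8.2.4, define the platelet and ANC baseline for HI-P and HI-N, for both the entry cut-off and the response reference, as the mean of at least two counts not influenced by transfusion, at least one week apart, within 28 days before the applicable Cycle 1 Day 1 (A536-03 for patients without interruption, A536-05 for those with). In addition:

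- State whether the pre-dose Cycle 1 Day 1 sample may be one of the counts. Allowing it seems reasonable, but it is a reading of the footnote.
- Give the transfusion exclusion window for platelets. The documents specify one for hemoglobin only.
- Use a single count only where no second qualifying one exists; flag those patients and report their number.
- List this fallback and any other departure from Appendix 5 in 5.13. If the last-value rule is kept, declare and justify it there and add the averaged baseline as a sensitivity analysis.

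The cost is SAP wording and programming. Hematology with platelets and white-cell differential is already scheduled at Screening and Cycle 1 Day 1 in A536-03 (SAP Appendix 2) and, for patients with interruption, in A536-05 (Protocol Section 2; SAP 5.8.7). The number of patients with only one qualifying count is unknown, because the one-week spacing of draws is not required for platelets or ANC. Reported rates will be somewhat lower: adding an assumed 20% of true responders (ANC x 2.5, platelets +60) to the central simulation, reported HI-N falls from 30% to 22% and HI-P from 31% to 24%.
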